## **DATA MANAGEMENT AND CONFIDENTIALITY**

Each participant will be assigned a study ID consisting of the participant's numerical code. Subjects name will not be recorded on study materials, except on the consent form. Signed Consent forms with the participant's full name and signature will be kept by the study coordinator separately from other study files double-locked and secured at the research offices. In the electronic database, the data will be saved and identified with an assigned study number; patient's name or data that can potentially lead to identification of the patient will not appear in the database. The results of this study may be used for publication but will not include subjects' name. The study materials and documentation will be kept for 3 years after closure of the study.

## **SAFETY MONITORING PLAN**

### **tDCS safety data**

As per FDA determination, tDCS is considered a non-significant risk technique, and was exempt from the IDE requirement.

The safety of this technique has been addressed and tested by multiple researchers. To date, more than 100 studies have been reported in electronically accessible databases (MEDLINE, PUBMED) on effects of tDCS, underlying mechanisms, and safety in humans (Ardolino et al., 2005; Lang et al., 2005; Nitsche et al., 2003a,b; Liebetanz et al., 2006). Notably, tDCS has been shown to comply with general safety considerations as delineated for all types of non-invasive transcranial electrical stimulation (Agnew and McCreery, 1987; Nitsche et al., 2003a,b). Beyond the general safety parameters of the tDCS technique, safety considerations pertaining to tDCS stimulation parameters has been observed to ensure the safety of participants undergoing tDCS stimulation. Major safety parameters of electrical stimulation utilizing direct current (as opposed to devices producing alternating current), are Current Density [A / cm^2] = stimulation strength [A] / electrode size [cm^2], and Total Charge [C/cm^2] = stimulation strength [A] / electrode size [cm^2] x total stimulation duration [s] (Nitsche et al., 2003a,b). Therefore, these major safety parameters are determined by the size of the electrodes, the intensity of the current and the duration of the stimulation. A comprehensive review on safety of tDCS in human subjects by Sundaram et al. (2009) evaluated all existing tDCS protocols involving human participants for the aforementioned safety parameters, Current Density and Total Charge, as well as available data from animal studies identifying potentially damaging values for each parameter: the threshold for potentially damaging Current Density was at 25 mA/cm^2. The threshold for potentially damaging Total Charge was 216 C/cm^2. Notably, tDCS protocols involving human subjects typically apply tDCS at the intensity of 1-2mA, for 10-30 minutes, with electrodes of size 25-36 cm^2. This translates into Current Density 0.03-0.08 mA/cm^2 and Total Charge 0.018-0.096 C/cm^2, thus orders of magnitude below the potential safety threshold. The parameters in our study will be: the current intensity 1.5 mA, for 20 minutes, with electrodes of size 25cm^2. Thus, Current Density will be 0.06 mA/cm^2 and Total Charge 0.072 C/cm^2, which is within the parameter range delivered in other tDCS studies and well within safety limits.

Researchers at the National Institute of Neurological Disorders and Stroke (NINDS) conducted a safety study on tDCS, investigating 20-minute sessions of 1 mA and 2 mA current stimulation with healthy controls (n=103), and no negative effects were identified (Iyer et al., 2005).

In a review of 567 tDCS sessions conducted over a period of two years, Poreisz et al. (2007) reported that during tDCS, a mild tingling sensation was reported by 70.6% subjects and a light itching sensation under the stimulation electrodes occurred in 30.4% cases (Poreisz et al., 2007). It is important to note that a mild tingling/itching non-painful sensation during tDCS is a natural sensation pertaining to passing the electrical current through the skin, similarly as water-flow elicits non-painful sensation on the skin surface. Other events reported in Poreisz' study were transient headache, and infrequently reported nausea and insomnia. Some subjects in Poreisz study also reported fatigue during and after tDCS, while subjects in another study experienced a fatigue improvement (Bocci et al., 2013).

Overall, the most common side effects reported in tDCS studies were: headache, dizziness, nausea, itchy sensation as well as transient irritation under the area of the electrodes (Brunoni et al., 2011; Brunoni et al., 2012; Iyer et al., 2005; Poreisz et al., 2007). Thus, a growing body of research from different laboratories support the notion that tDCS is a noninvasive technique for modulating neural excitability, with favorable safety profile.

#### Monitoring of Subjects and Criteria for Withdrawal of Subjects

**Adverse Events (AEs):** Study personnel will monitor study participants for AEs thorough the course of the study, and in 30-day post-study safety follow-up by phone.

Any AE that is ongoing at the time of the participant's study completion or withdrawal will be followed by the study physician and PI until the event resolves or stabilizes.

AEs will be captured, by the Investigator or designee, in the subject's source documents and on the case report form (CRF). AEs will be followed by the study physician and Principal Investigator and reported to the IRB in accordance with regulatory requirements.

Fluctuation of intensity and frequency of symptoms evaluated in the study is expected due to natural course of the chronic illness. If the patient reports significant worsening of any symptom during treatment, this will be conveyed to the study physician, who will assess the patient's report and offer the patient appropriate follow-up.

The participant may withdraw from the study at any point for any reason.

Participants may be removed from the study for the following reasons:

- Not following the study protocol or instructions from study personnel.
- Participants who during familiarization (Visit 2) find the sensory sensation associated with the stimulation unacceptable.
- Participants who after instruction are not able to perform tDCS in accordance with the procedure described in the patient's instructional booklet.

- If a serious adverse event related or potentially related to the study procedure occurs.
- If the study closes.

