## **OUTCOME MEASURES AND ENDPOINTS**

Outcome assessment time-points will be at the end of the 30-day baseline ( $\pm 2$  days), at the end of month 1 (day  $30 \pm 2$  days, the secondary end-point) and month 2 (day  $60 \pm 2$  days, the primary end-point) of the tDCS/sham intervention.

The primary comparison will be the between-group comparison at the end of month 2 of the tDCS/sham intervention.

**The primary outcome measure** will be *Change in mean number of migraine days per month.*

A note: A migraine day is defined as any calendar day on which the patient had onset, continuation, or recurrence of a migraine as recorded in the diary. A migraine is defined as a migraine (with or without aura) lasting at least 30 minutes. Any calendar day on which acute migraine medication is used is counted as a migraine day.

**Secondary outcome measures** will be:

1. *Percentage of responders*, determined as a number of patients having at least 50% reduction of monthly migraine days between the one-month baseline and post-intervention, in each of the two study groups;
2. *Change in monthly migraine attack frequency*,
3. *Change in monthly acute antimigraine drug use*,

all determined from the patients' diaries;

4. *Change in mean headache severity per migraine day* determined from Pain NRS ratings on migraine days;
5. *Change in quality of life* determined from ratings on the migraine-specific MSQ questionnaire;
6. *Change in depressive symptoms* determined from the Hamilton Depression Scale (HamD);
7. *Tolerability* determined from occurrence of side effects and adverse events related, probably related or possibly related to tDCS, through the study;
8. *Satisfaction* - percentage of patients stating at the end of the trial that they are very satisfied, moderately satisfied, or not satisfied with the treatment, determined from the 8-item tDCS User Survey at the end of the intervention;

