### *Outcome Assessment*

Outcome assessment will utilize the following tools:

- Patients's Daily Diaries will be used to take notes of days on which a migraine attack occurs, duration of the attack, severity of migraine pain during the migraine attack, acute antimigraine drug use, and occurrence of any other (non-migraine) headache. Time needed to fill-in the diary is about 1-3 minutes per day (filled-in only on days when headache or migraine medication intake occur).
- Pain Numerical Rating Scale (Pain NRS) is an eleven point [0-10] scale for rating of pain intensity, with the anchor points 0=no pain and 10=worst pain imaginable. Administration time is about 1 minute, rated only on migraine days.

- Migraine-Specific Quality of Life Questionnaire (MSQ) is a validated 25-item questionnaire evaluating impact of migraine on physical, emotional and social component of patients' life. Recall period is four weeks. Administered at the baseline, at the end of month 1 and month 2 of tDCS/sham application. Administration time is about 5 minutes (Rendas-Baum et al., 2013).
- Hamilton Depression Scale (HamD) is a validated 17-item instrument for assessment of depressive symptoms. Administered at the baseline, at the end of month 1 and month 2 of tDCS/sham application. Administration time is about 20 minutes (Hamilton, 1960; Williams, 1988).
- tDCS User Survey is an 8-item questionnaire on user's satisfaction with the use of tDCS. Administered at the end of tDCS use. Administration time is about 5 minutes.
- Occurrence of side effects and adverse events through the study. Tolerability will be determined from occurrence of side effects and adverse events related, probably related or possibly related to tDCS, through the study.

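### A stimulation headache can count as a migraine day, but no stated criterion or prespecified analysis ensures that it also counts towards tolerability

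*Protocol*

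**What the plan says.** **Headache as a side effect.** The Protocol, under tDCS safety data, states that "the most common side effects reported in tDCS studies were: headache, dizziness, nausea, itchy sensation" and local skin irritation. It gives no rate for headache.

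**Headache in the efficacy outcome.** Under Outcome Measures and Endpoints the primary outcome is "Change in mean number of migraine days per month". A migraine day is "any calendar day on which the patient had onset, continuation, or recurrence of a migraine as recorded in the diary". The definition of migraine adds a 30-minute minimum duration and says nothing about cause or about timing relative to a session. A second rule follows: "Any calendar day on which acute migraine medication is used is counted as a migraine day".

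**Headache in the safety outcome.** Tolerability, in the same section, counts side effects and adverse events judged at least possibly related to tDCS. Under Monitoring of Subjects, adverse events are monitored throughout and entered on the case report form, and significant worsening of a symptom goes to the study physician. That section also says "Fluctuation of intensity and frequency of symptoms evaluated in the study is expected due to natural course of the chronic illness".

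**The diary.** Under Outcome Assessment, patients also note "occurrence of any other (non-migraine) headache". No safety or tolerability measure in either document uses that field.

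**The SAP.** Its text compares all, serious and treatment-attributed adverse events between arms. The Tolerability row of its table covers side effects, total adverse events and those related to treatment in any degree. It has no rule or row for headache.

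**The concern.** Headache is both a known effect of the device and the symptom the device is meant to reduce. The plan says how a headache becomes an efficacy event. It does not say how one becomes a tolerability event. Aim 1 covers efficacy and safety together, so one gap touches both halves. A device headache could count against efficacy and be missing from the safety tables. A trial with no difference in migraine days would then be harder to interpret: less prevention, or some prevention offset by headaches from the sessions.

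**Working it through.** The documents contain no figure on this point to reproduce, so the check traces a headache through the rules and then shows a scale under stated assumptions.

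**Step 1. Three routes for a headache caused by a session**

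- *Treated with acute migraine medication.* It is a migraine day by the medication rule, whatever its cause.
- *Untreated, at least 30 minutes long, and recorded by the patient as migraine.* It is a migraine day by the diary rule.
- *Untreated and noted as another headache.* It is not a migraine day. It enters the diary field, which no analysis uses.

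On all three routes, reaching Tolerability requires that someone records the headache as a side effect or adverse event and judges it at least possibly related. Neither document says when a diary headache must be recorded in that way, or how to attribute it to tDCS or to migraine. Timing relative to the session would inform that judgement, but it is not among the diary contents listed under Outcome Assessment.

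**Step 2. Does the SAP close the gap?** Its all-adverse-event comparison removes the relatedness judgement but not the recording step. A headache that exists only in the diary is not in that comparison.

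**Step 3. Would the effect cancel?** Not through change from baseline: there are no sessions in the 30-day baseline and one a day during the intervention. Between arms it cancels only if session headaches are equally frequent. Active delivers 20 × 60 = 1,200 seconds at 1.5 mA and sham 30 seconds (Protocol, tDCS stimulation protocol and device), a ratio of 1,200 / 30 = 40. A higher rate with active is therefore plausible, but the documents do not show it.

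**Step 4. Scale, by assumption.** Let h be the probability that a session causes a headache that turns an otherwise migraine-free day into a migraine day. This is a joint probability, so the underlying headache rate would be at least as high. With about 30 sessions per 30 days:

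extra migraine days = 30 × h

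A responder must fall by at least 50%, so may keep at most 4 × 0.5 = 2 days at the entry minimum of 4, or 15 × 0.5 = 7.5 days from a baseline of 15.

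| h (assumed) | Extra days per 30 | Share of the 2-day allowance | Share of the 7.5-day allowance |
|---|---|---|---|
| 1% | 0.3 | 15% | 4% |
| 3% | 0.9 | 45% | 12% |
| 5% | 1.5 | 75% | 20% |
| 10% | 3.0 | 150% | 40% |

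The average distortion between arms is 30 × (h in active − h in sham), so the second column is the full distortion only if h in sham is zero. For a single patient at the entry minimum, one added day changes 4 to 2 (2/4 = 50%, responder) into 4 to 3 (1/4 = 25%, non-responder).

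**The case against.** The case against is substantial, and several stronger readings fail.

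- **That the fluctuation sentence takes headaches out of adverse-event recording.** It does not. It calls fluctuation expected, in a section that also requires adverse-event monitoring. Nothing stops one headache being both a migraine day and an adverse event. The gap is a missing rule, not an exclusion.
- **That staff have no basis for attributing a headache to the device.** Possible relatedness is a low bar, and the Protocol itself names headache as a side effect. The first session is supervised in person, and remote contact is at least three times in the first week and at least twice a week afterwards. Staff can ask about timing. What is missing is a criterion that makes them do so consistently.
- **That the added days fall in the active arm only.** Sham also delivers brief current daily, and sham users may report and treat headaches. Any bias is conditional on a difference between arms.
- **That headache is the main side effect.** This reads frequency into list order. The only rates given are for tingling (70.6%) and itching (30.4%). The Protocol also cites a study of 103 healthy controls in which no negative effects were identified, so the headache rate may be low.
- **That the trial cannot separate lack of prevention from device headache.** The diary already records non-migraine headache, attack duration, severity and drug use, so part of the separation can be recovered. What is missing is a prespecified analysis and the timing of onset.
- **That every headache after a session should be an adverse event.** With daily sessions this would capture nearly every migraine. At the entry minimum, 60 patients × 4 days × 2 months = 480 migraine days if nothing changed, enough to swamp the tolerability signal.

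What survives is narrower: the efficacy route is fixed by rule, the tolerability route is left to unstated judgement, and a relevant field already collected goes unused.

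**Conclusion.** The concern holds in a limited form. By the Protocol's own definitions, a stimulation headache treated with acute migraine medication is a migraine day. Whether it is also a tolerability event depends on recording and attribution for which no criterion is given, and the SAP's comparison of all adverse events helps only once the headache has been recorded.

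The direction is conditional. If session headaches are more frequent with active than with sham, tolerability could look too favourable and the primary comparison could be biased toward no effect. The size is unknown. The range of 0.3 to 3.0 days per 30 rests on an assumed h of 1% to 10% that nothing in the documents anchors, and the responder example uses the most sensitive baseline. This is an inexpensive improvement worth making before data collection, because onset relative to a session cannot be reliably reconstructed later. It does not invalidate the primary outcome.

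**What to change.** 1. **Use the field already collected.** Add to Tolerability in the Protocol, and to the SAP table, a comparison by arm of diary non-migraine headache days per 30 days. It needs no relatedness judgement. State that a day counts here even if the medication rule also makes it a migraine day.
2. **Record timing.** Add one diary item: did a headache begin within a short window, fixed in advance, from the start of the session? Compare these headaches by arm as a tolerability measure, without making every headache after a session an adverse event. Ordinary migraines will fall in the window in both arms, so the excess in one arm is what informs.
3. **Test the primary result.** Keep the migraine-day definition for the primary analysis. Add one sensitivity analysis that leaves out days qualifying only through medication use, at baseline and at month 2 alike. Report with it that this may also drop genuine migraines treated early, and that it does not remove session headaches the patient recorded as migraine; item 2 gives information on those.

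The cost is one diary item, completed only on days when the diary is filled in anyway, two rows in the SAP table and one sensitivity analysis. Treatment, visits and sample size do not change.

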## STUDY PROCEDURES AND METHODS

### Procedural schema

Event/Time	Procedures
Visit 1	Consenting, Screening, Baseline Daily Diaries dispensed
30-Day Baseline	Baseline Daily Diaries kept Study eligibility affirmed
Randomization	In double-blind manner to active tDCS or sham tDCS
Visit 2 (within 3 days after randomization)	Questionnaires MSQ and HamD administered tDCS familiarization, training, equipment dispensing First tDCS/sham self-application under in-person supervision of study personnel
Daily tDCS/sham at home for 60 days	Daily Diaries kept Interim outcome assessment in remote on Day 30±2 of tDCS/sham: Questionnaires MSQ and HamD, Daily Diaries evaluation
Visit 3 (within 3 days after tDCS/sham completion)	End-of-study outcome assessment: Questionnaires MSQ, HamD, tDCS User Survey, Daily Diaries evaluation, AEs evaluation Equipment collected Monetary compensation for time and effort dispensed
Post-study safety follow-up (for 30 days after last tDCS/sham)	Two bi-weekly phone calls

**Recruitment:** The study will include general public – adult men and women living at home (not at an institution, such as nursing home etc) in boroughs of New York City and its suburbs. The study plans to randomize 60 patients. In order to account for screen failures and possible drop out during the baseline period prior randomization, it is anticipated that about 75 patients will have to be consented and screened.

The main source of referrals will be from staff of the New York Headache Center (Sub-investigator [name]). Other recruitment outreach will include patients' self-referrals through IRB-approved flyers/advertisement material disseminated in boroughs of New York City and its suburbs.

Upon the initial contact, patients will be asked if they wish to receive information about the study. If yes, study personnel will provide detailed information and answers questions. Patients will be given enough time to consider the study participation. If a patient expresses interest in participating in the study, the study personnel will schedule the initial visit (Visit #1).

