Upon conclusion of the first and second month of the tDCS intervention, the patient will provide answers to the quality of life questionnaire (MSQ), Hamilton Depression Scale, and to the 8-item tDCS User Survey (at the end of the second month only). as well as his/her impression of having received either active or sham treatment, in order to evaluate the blinding. **Visit #3 – Device Return** will be held either at the patient's home or at a designated room at the MJHS Institute, whichever is more convenient for the patient, upon conclusion of the study intervention. At the visit, patients will answer to the questionnaire package including MSQ, HamD, and tDCS User Survey. tDCS device and remaining study materials and supplies will be collected, and the patient will receive monetary compensation for time and effort associated with the study intervention procedures (see in detail below, section Administrative Issues – Compensation).

**Safety Monitoring** will be carried out throughout the study in accordance with the Safety Monitoring Plan (described in detail below) and will continue bi-weekly by phone for 30 days after the last tDCS/sham application.

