## **SAMPLE SIZE DETERMNATION AND DATA ANALYSIS**

The sample size calculations are based on responder rates from previous studies of non-invasive neurostimulation in migraine (Lipton et al., 2010; Saper et al., 2011). The numbers used were 15% for sham, based on published trials and 55% for the supraorbital neurostimulation inferred from the pilot study (Gerardy et al., 2009; Lipton et al., 2010; Saper et al., 2011) and 12.1% for sham vs 38.1% for verum in the RCT (Schoenen et al., 2013). To detect a significant difference between the 2 treatments (5% significance level) with an 80% power, the minimum size of each treatment group was estimated at 26 patients, 52 in total who get randomized and initiate the intervention. To account for possible dropouts in the category "randomized, but never started the intervention", we plan to randomize in total 60 patients. To account for patients who do not meet the eligibility criteria at screening, we anticipate we will need to consent about 75 patients.

Statistical analysis will be carried out on an intention-to-treat basis, as well as per protocol for comparison. For Aim 1, the primary comparison will be the between-group comparison at the end of month 2 of the tDCS/sham intervention for the primary and secondary outcomes measures (listed in detail on pgs 7,8). Secondary exploratory comparisons will include between-group comparisons at the month 1 (Day-30) of the 2-month intervention, and within groups comparisons across the study time-points (the baseline, month 1, month 2), as well as comparison of efficacy in patients with chronic and episodic migraines and comparison of efficacy in patient taking abortive migraine medications on 10 or more days with those taking them on 9 or fewer days.

For Aim 2, (Satisfaction with the device and procedure), the primary analysis will include the between-group comparison of at the end of month 2 of the tDCS/sham intervention, evaluating the percentage of patients stating at the end of the trial that they are very satisfied, moderately satisfied, or not satisfied with the device use and procedure, determined from the 8-item tDCS User Survey at the end of the intervention. (We anticipate significant group differences in Survey items pertaining to being more confident in symptom management at home, but no significant group differences in items pertaining to satisfaction with tDCS training and ease of use of the device). In addition, the

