process data - number of delivered applications and the protocol fidelity in each study group will be analyzed, in order to support evidence on feasibility of the procedure.

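### Participants may be removed from the study, not only from stimulation, for non-adherence, with no provision for outcomes after early stopping, so month-2 data may be missing where the intention-to-treat analysis needs them

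*Protocol*

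**What the plan says.** **Removal.** The Protocol section on monitoring and withdrawal of subjects opens its list with "Participants may be removed from the study for the following reasons". The reasons include "Not following the study protocol or instructions from study personnel" and "Participants who after instruction are not able to perform tDCS in accordance with the procedure described in the patient's instructional booklet". Removal is from the study, and no adherence threshold is given.

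**End-of-study assessment.** The Procedural schema sets Visit 3 "within 3 days after tDCS/sham completion". The Visit 3 narrative places it "upon conclusion of the study intervention. At the visit, patients will answer to the questionnaire package including MSQ, HamD, and tDCS User Survey". Design and Overview and Outcome Measures and Endpoints, by contrast, fix the primary end-point at day 60±2.

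**After an early stop.** The only follow-up described after the last application, or for a participant who withdraws, concerns safety: the phone calls over 30 days and the follow-up of ongoing adverse events. Neither document says that diaries, MSQ or HamD continue.

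**Analysis.** The Protocol states: "Statistical analysis will be carried out on an intention-to-treat basis, as well as per protocol for comparison". It adds that the "number of delivered applications and the protocol fidelity in each study group will be analyzed", as evidence on feasibility. The SAP says that missing values in the intention-to-treat analysis will be imputed from whatever data are available, names no method, and plans a comparison of outcomes at high and low compliance.

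**The concern.** An intention-to-treat comparison at month 2 needs a month-2 outcome from everyone randomised, including those who used the device little or stopped. The removal rule is aimed at exactly these participants. Once someone is out of the study, nothing in the documents keeps the diary going, and the diary is the source of the primary outcome.

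The loss could be informative, because adherence may depend on perceived benefit or on the sensation of stimulation. Active treatment is 20 minutes at 1.5 mA, while sham is 30 seconds followed by no current. The same rule could thin out the low-compliance group that the SAP wants to compare, and it would cut short the record of delivered applications. Data that were never collected cannot be recovered by a later SAP.

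**Working it through.** **1. The timeline for one case.** Take a participant removed on day 20.
- Diaries are sent in weekly by email or fax, so those up to removal exist. Days 31-60, the month-2 period, are not observed.
- If completion in the Visit 3 window means the last application, MSQ and HamD would fall on days 20-23, not on day 60±2. The MSQ recall period is four weeks, so an MSQ on day 23 would reach back to day 23 − 28 = −5, before the first application. If completion means the full course, no Visit 3 is triggered.
- Delivered applications are known to day 20 (at most 20 of 60).

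For a participant who uses the device for the full 60 days the two timings agree. They separate only when stimulation stops early.

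**2. The plan's own sample size.** Inputs from the sample size section: 15% vs 55% responders, 5% level (two-sided per the SAP), 80% power.
- Mean proportion 0.35; 2 × 0.35 × 0.65 = 0.455; 0.15 × 0.85 + 0.55 × 0.45 = 0.375.
- n = (1.96 × √0.455 + 0.8416 × √0.375)² / 0.40² = 3.376 / 0.16 = 21.1.
- With continuity correction: (21.1 / 4) × (1 + √(1 + 4 / (21.1 × 0.40)))² = 25.9, so 26 per group. This matches the plan.

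The plan randomises 60 rather than 52, a margin of 8/60 = 13.3%, but assigns that margin to participants who never start. Losses after starting have no allowance of their own.

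**3. What loss does to the observed data.** Exact power of Fisher's test (the SAP's test for responders) at 15% vs 55%, by number observed per arm:

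| Observed per arm | Loss from 30 | Power |
|---|---|---|
| 30 | 0% | 0.876 |
| 26 | 13.3% | 0.824 |
| 24 | 20% | 0.785 |

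These figures use observed values only and hold the responder rates fixed. They are not the power of an imputed analysis.

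**4. Illustration of bias, responder outcome only.** Let q be the fraction of the active arm removed, pA the rate among those retained and pS the sham rate. Assume that removed active participants truly respond at pS and are imputed at pA.
- True active rate = (1 − q) × pA + q × pS; rate after imputation = pA; overstatement = q × (pA − pS).

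| Pair in the Protocol | q | True active rate | After imputation | Overstatement |
|---|---|---|---|---|
| 55% vs 15% | 10% | 51% | 55% | 4 points |
| 55% vs 15% | 20% | 47% | 55% | 8 points |
| 38.1% vs 12.1% | 10% | 35.5% | 38.1% | 2.6 points |
| 38.1% vs 12.1% | 20% | 32.9% | 38.1% | 5.2 points |

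**5. The direction depends on the method.** Keep the same truth, assume no removal from sham, and count removed active participants as non-responders. The active rate becomes (1 − q) × 55% = 49.5% at q = 10% or 44% at q = 20%, against true rates of 51% and 47%. The difference is now understated by 1.5 or 3 points.

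The range for q is an assumption, because the documents give no removal rate.

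**The case against.** The strongest reply is that the plan already expects poor adherers to stay. Removal is permitted, not required. A high/low compliance comparison, and an intention-to-treat analysis beside a per-protocol one, make sense only if low users remain. The Compensation section withholds payment from non-adherers, which can be read the same way. The end-point is already day 60±2, and the primary outcome comes from weekly diaries rather than from Visit 3. All of this stands. It limits the concern to participants who are actually removed or who stop early, but for them it supplies no provision.

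A reader might infer more than the documents support:
- **That month-2 outcomes are bound to be lost.** The rule is discretionary, so loss is possible, not automatic.
- **That the Visit 3 timing costs the primary outcome.** Removal from the study would end the diary. The Visit 3 timing mainly affects MSQ, HamD and the User Survey.
- **That imputation will treat removed participants as continuing users and pull the intention-to-treat result towards the per-protocol result.** The SAP names no method. The available data include the participant's own baseline and pre-removal diaries, and those of retained low compliers.
- **That fidelity will look better than it was.** A truncated count lowers a mean taken over everyone randomised. It flatters fidelity only if removed participants are dropped or the denominator is shortened, and neither is stated.
- **That removal will differ by arm.** This is plausible, but no figure in the documents shows it. The SAP does plan to compare attrition between groups.

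**Conclusion.** The concern holds as a gap in the design. The Protocol allows removal from the study for non-adherence or inability to perform the procedure, and neither document says how month-2 outcomes are obtained afterwards. Diary data and questionnaires may then be missing, possibly informatively, for participants needed by the intention-to-treat and compliance analyses. Delivered-application data would be truncated rather than lost.

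The size is not known. The illustrative overstatement of 4-8 points, or 2.6-5.2 points with the smaller effect, rests on three assumptions together: 10-20% of the active arm removed, a true response at the sham rate, and imputation like retained participants. It concerns a secondary outcome. Nothing has been quantified for the primary outcome, change in migraine days by Mann-Whitney U, and another imputation rule can reverse the sign.

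**What to change.** - **Monitoring and withdrawal section:** separate stopping the device from leaving the study, without changing any stopping reason. Unless consent to data collection is withdrawn or the study closes, participants who stop the device continue the weekly remote diaries. They also complete the day-30 and day-60 MSQ and HamD by the remote route already used at day 30.
- **Procedural schema and Visit 3 narrative:** tie the end-of-study assessment to day 60±2 from first application, whether or not stimulation continued, in line with Design and Overview and Outcome Measures and Endpoints.
- **Data collection:** record the date and reason for device stop, and count delivered applications to day 60 over all randomised participants.

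The cost is a protocol and consent amendment and a few more weeks of reminders for those who stop early. Some of them will decline to continue diaries, so the change reduces missing data but does not remove it. The required 26 per group is unaffected.
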